period of 40 minutes. **We will conduct an open label, naturalistic study focusing on the antidepressant effects of ketamine twice a week for the first 4 weeks and then weekly injections up to week 8 in an academic psychiatric hospital (UTHealth Harris County Psychiatric Center - HCPC).** Thirty patients with clinically documented TRD will be screened for diagnosis with the depression and bipolar disorder subset of the Structured Clinical Interview for DSM-IV (SCID) (First et al., 1996) at baseline to establish the presence of a major depressive episode.

The administration of ketamine and urine tests will be carried out at the UTHealth Harris County Psychiatric Center (HCPC) in Houston, Texas. Routine blood tests and clinical/cognitive assessment will be done at the UTHealth Harris County Psychiatric Center (HCPC). Study drug will be provided in identical syringes, containing clear solutions including 1 mL of ketamine, e.g. 100 mg/mL with 9 mL of normal saline. A syringe will be used to provide IV applications of solution (). An ACLS psychiatrist will monitor the patient at HCPC. The administration of ketamine will be initiated by the anesthesiologist. The anesthesiologist will be present during the ketamine administration (40 minutes) and post-procedure (until patient is awake and anesthesiologist deems patient is clinically stable. The infusions will be conducted in our hospital during the mornings in a room set specially for this study. During the infusion, patients will be asked constantly about -how they feel and will receive constant attendance from a psychiatric nurse and the attending ACLS- trained psychiatrist. ECG and pulse oximetry monitoring will be maintained throughout the infusions to check for hemodynamic changes.

After completion of each 40 minute infusion, patients will rest for 2 hours under observation of the clinical nurse before being discharged to a responsible adult who will accompany the patient home. Based on Zarate et al.'s (2012)'s protocol infusions will be administered twice a week, every 3 days for the first 4 weeks of the treatment period.

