Routine blood tests will be performed in fasted state before the first ketamine infusion, prior to infusions at week 4 and at week 8. These tests aim to test the participants' overall health state. Blood samples will also be used for genetic testing and to measure levels of inflammatory markers. Samples will be stored at [REDACTED]. As stated in the consent form, participants will not receive any medical results or genetic counseling by providing a sample. All participants will undergo urine drug tests before each ketamine infusion.

Clinical questionnaires (e.g. MADRS) will be administered at baseline, at weeks 4, 8, and Week 12. The PANSS and Q-LES-Q scale will be administered after each ketamine infusion is completed. During the course of infusions, patients will receive treatment-as-usual from their primary psychiatrists as would be the case in a traditional therapeutic setting. There will be no changes in medication regimen throughout the 8 week treatment period as well as the 4 week observational follow-up period. Participants will be provided with a contact card directing them to the nearest ER/physician in case of emergency. Participants will be contacted weekly during the 4 week observational period to review the patient's health status and administer clinical scales. Upon conclusion of the intervention patients will be offered the opportunity to come back for maintenance sessions. The frequency of these sessions will depend on the patient's wishes and the physician's clinical judgment. The maximum session frequency will be once every month for a maximum of 12 months.

Assessment

The protocol consists of two components: clinical and cognitive assessments.

Clinical assessment

This evaluation will obtain family history and demographic data. Copies of any recent medical evaluations (past medical history, physical exam, etc.) will be requested from treating clinicians and health care providers. We will perform a urine drug screening (UDS) to rule out recent undisclosed use illicit substances. Demographic information is obtained through a standardized form and covers: age, race, gender, education (information both on siblings and their parents), religion, and socioeconomic status. Participants will fill out mood questionnaires rating the severity of the clinical symptoms.

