-MINI Interview: This is the standard psychiatric research evaluation for ascertainment of psychiatric diagnosis in the context of research studies (Sheeha et al., 2016)). It is a comprehensive structured interview for determining axis I diagnosis according to the DSM-V.

-Clinical Global Impression Scale (CGI): This is a clinical instrument to assess global changes in patients' status in clinical studies. We will use the CGI-BD, for use with BD patients (Guy et al., 1976).

-Montgomery-Åsberg Depression Rating Scale (MADRS): this scale rates depressive symptoms, and its psychometric properties are well-established (Montgomery et al. 1979).

-Young Mania Rating Scale (YMRS): This is a well-established clinical severity rating scale for manic symptoms that has adequate inter-rater reliability and internal consistency (Young et al., 1978).

- Quality of Life Enjoyment and Satisfaction Questionnaire (Q-LES-Q): this scale is patient-reported and measures the degree of enjoyment and satisfaction experienced by subjects in various areas of daily functioning (Endicott et al., 1993).

-

- The Positive and Negative Syndrome Scale (PANSS) includes 30- items and was conceived as an operationalized, drug-sensitive instrument that provides balanced representation of positive and negative symptoms. It is composed of four scales measuring positive and negative syndromes, their differential, and general severity of illness. The Positive and Negative Syndrome Scale (PANSS) for Schizophrenia. Kay, Stanley R.; Fiszbein, Abraham; Opfer, Lewis
A. Schizophrenia Bulletin, Vol 13(2), 1987, 261-276. This scale will be administered following each ketamine infusion to assess acute changes in mood.

Self-report questionnaires to assess mood and anxiety:

1. Adult (Brief Dissociative Experiences Scale [DES-B]—Modified): Frequency: After every injection, to monitor the dissociative side effects, Scale features: simple, easy to use, new DSM-5 self-rated scale
2. Severity Measure for Generalized Anxiety Disorder—Adult : Every 4 weeks, to measure the severity of anxiety. Scale features: simple, easy to use, new DSM-5 self-rated scale
3. Snaith–Hamilton Pleasure Scale: every 4 weeks, to measure the level of anhedonia, Scale features: easy to use, used before in ketamine studies, self-rated scale

Cognitive assessment

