- 12) Pregnancy or Breast feeding. All female in reproductive age will undergo pregnancy tests. Female participants will be required to provide evidence of use of contraceptives during the course of the study.
- 13) Unable to understand the design and requirements of the study
- 14) Unable to sign the informed consent for any reason
- 15) An assigned responsible adult has provided assent to assist in patient's study participation. The responsible adult agrees to be present at each study appointment as well as provide transportation to study appointments for the patient.

Non responders

If a patient does not respond to the study treatment by their 4th treatment they will be removed from the study due to non-response. A successful response to study treatment will be at least a 30% reduction in MADRS scores from screening until the 4th treatment. Again if a patient does not respond by the 4th treatment, they will be excluded from the study.

Unanticipated Hospitalizations

If a patient needs to be hospitalized for worsening of symptoms or for their own personal safety, they will be removed from their study participation and their study treatment will end at that time.

Feasibility

Subject recruitment: Our center has access to a large patient pool (drawing from a metropolitan area of about 5.5 million people) and well-established ability to recruit patients with mood disorders. [name] is the department chair for Psychiatry and Behavioral Sciences and Director of the University of Texas, Center of Excellence on Mood Disorders. He successfully completed a large number of studies over the past 20 years with excellent recruitment of MDD and BD subjects at this site. We will also recruit participants through doctor referrals. Participants will be exclusively outpatients.

Funding of the study: given the preliminary nature of this study we plan to use departmental funding for the current study and then possibly apply for a larger grant later on once we have collected preliminary data and calculated optimal power/effect sizes for ketamine treatment in individuals with TRD.

Data analysis

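### Treatment-4 non-responders leave the study at about week 2, before the first scheduled follow-up MADRS at week 4, so MADRS change at scheduled visits describes early responders and overstates improvement in all treated patients

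*Combined protocol and SAP*

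**What the plan says.** All passages are in section 2.0 of the combined protocol and SAP.

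- **Removal for non-response** (paragraph headed Non responders) is worded as follows: "If a patient does not respond to the study treatment by their 4th treatment they will be removed from the study due to non-response". The threshold is: "A successful response to study treatment will be at least a 30% reduction in MADRS scores from screening until the 4th treatment". The section then repeats that "if a patient does not respond by the 4th treatment, they will be excluded from the study".
- **Removal for hospitalisation** (Unanticipated Hospitalizations): for patients admitted for worsening or for their own safety, "they will be removed from their study participation and their study treatment will end at that time".
- **Timing of infusions** (C. Approach): "infusions will be administered twice a week, every 3 days for the first 4 weeks of the treatment period".
- **MADRS schedule** (C. Approach): "Clinical questionnaires (e.g. MADRS) will be administered at baseline, at weeks 4, 8, and Week 12". The Study design table has the same visits plus the weekly follow-up calls. Its after-each-infusion column has no MADRS.
- **Scales taken at every infusion** (C. Approach; self-report questionnaires): "The PANSS and Q-LES-Q scale will be administered after each ketamine infusion is completed", and the dissociation scale "After every injection, to monitor the dissociative side effects".
- **Analysis** (Data analysis): paired t tests between two time points, random effects models of clinical scores over time, splines over the whole sample, and trajectories of eventual responders against non-responders. No analysis set, missing-data rule or remission denominator is given.
- **Purpose** (Study design): to produce an effect size for a later randomised trial or grant application. The primary outcome is remission on the MADRS (end of section A).

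**The concern.** The removal rule acts on the outcome itself, and it acts before that outcome is next scheduled to be measured. A patient who improves by less than 30% at treatment 4 leaves with a baseline MADRS and nothing later on the schedule. That patient cannot enter a paired change to week 4, 8 or 12, and adds no change information to a random effects model fitted to scheduled visits only.

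The score that decides removal must be taken for the rule to work, but it is neither in the schedule nor named in the analysis. (The screening score may simply be the scheduled baseline score.) The plan also cannot deliver what Data analysis promises: a pattern over time in the whole sample, and a comparison with non-responders, when treatment-4 non-responders have no later scheduled MADRS.

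At stake is the effect size carried into the next trial. It would describe patients already selected for early improvement, while the objective and hypotheses concern treatment-resistant patients receiving the infusions, without that restriction.

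**Working it through.** **1. Timing.** The schedule gives 2 × 4 + 1 × 4 = 12 infusions, which matches the 12 charged for under Reimbursement. At two per week the 4th falls by the end of week 2 (4/2 = 2). At 3-day spacing it falls on day 10 (days 1, 4, 7, 10). Either way it is roughly two weeks before the week-4 MADRS.

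**2. Direction.** Let π be the share retained, c the standardised cut-off at treatment 4, ρ the correlation between treatment-4 and later change, and SD the standard deviation of later change. Under normality, retained mean minus all-patient mean is

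bias = ρ × SD × φ(c)/π.

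This is positive whenever ρ > 0 and zero when ρ = 0.

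**3. Inputs for size.** The documents give no SD, correlation, baseline mean or remission cut-off. Assumed: SD of percentage reduction 30 points; ρ 0.4-0.8; baseline MADRS 32 (SD 6); week-8 mean reduction 5 percentage points better than at treatment 4; remission at MADRS ≤10. Early response is anchored on the low-dose serial-infusion study in Background and Rationale: 50% remission within at most four infusions in 10 patients, exact 95% CI 19-81%. That study used another dose and rate, and the remission scale is not given. Mean treatment-4 reductions of 40.5, 67.7 and 94.9% reproduce treatment-4 remission of 19, 50 and 81%.

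**4. By hand.** The SD of change is about 0.30 × 32 = 9.6 points, and c = (30 − mean)/30.

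- 19%: c = −0.35, π = 0.637 (19 of 30), φ/π = 0.375/0.637 = 0.589. Bias = 0.589 × 9.6 × (0.4 to 0.8) = 2.3 to 4.5 points.
- 50%: c = −1.26, π = 0.896 (27 of 30), φ/π = 0.181/0.896 = 0.202. Bias = 0.8 to 1.6.
- 81%: c = −2.16, π = 0.985 (29-30 of 30), φ/π = 0.038/0.985 = 0.039. Bias = 0.15 to 0.30.

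**5. Simulation** (same inputs, reductions capped at 100%, baseline floored at 20, at least 300,000 patients per scenario). The cap explains the slightly lower figures. The reference is change had all patients continued; d is the pre-post standardised change.

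| Treatment-4 remission | Retained of 30 | Mean change too high (points) | d too high | Remission, retained / all |
|---|---|---|---|---|
| 81% | 29-30 | 0.1-0.2 | 1-4% | 1.01 |
| 50% | 27 | 0.7-1.4 | 6-18% | 1.06-1.11 |
| 19% | 19 | 2.2-4.5 | 20-58% | 1.29-1.53 |

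With SD 20-40 and a remission cut-off of 10-12, the excess in d is 0-13%, 1-44% and 6-156% respectively.

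**6. Denominator.** If 16 remit and 27 are retained: 16/27 = 59% (exact 95% CI 39-78%) against 16/30 = 53% (34-72%). If 5 remit and 17 are retained: 5/17 = 29% (10-56%) against 5/30 = 17% (6-35%).

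**7. Would a model repair it?** Take mean reductions of 35% at treatment 4 and 40% at week 8, ρ 0.6. All-patient change is 12.7 points (d 1.29) and retained-only 16.7 (d 1.88). A likelihood model on baseline and week 8 also gives 16.7. Adding the treatment-4 score with unstructured covariance gives 12.8 (d 1.31). A random intercept with that score is not enough: at ρ 0.4/0.6/0.8 it leaves errors of 0.9/2.1/3.3 points, against 2.6/3.9/5.3 for the paired analysis.

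**The case against.** Five points on the other side have weight.

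- **Early response may be common.** Background and Rationale describes a study at this dose and rate in which 9 of 10 patients met the response criterion after the first infusion. That points to the small end. But those patients had already responded to a single ketamine dose, so it is an optimistic bound.
- **The analysis wording is general.** Data analysis does not name MADRS or visits for the paired tests. This stands: the bias arises when that wording is applied to the scheduled MADRS visits, which are the only ones listed.
- **A treatment-4 score will exist.** It must, for the rule to operate. But the plan does not schedule it or commit it to a model, and it cannot help a paired change to week 4, 8 or 12.
- **Removal need not mean discarding data.** This also stands. A reader might infer that the primary remission rate is inflated. The documents do not settle that, because no denominator is stated.
- **The all-continued target is not stated in the protocol.** True, and an uncontrolled pre-post d is not a between-arm effect in any case. If early responders were the intended target, the retained estimate would suit it, but the objective is not so restricted.

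Other stronger readings also go too far. Not every outcome is selected: PANSS, Q-LES-Q and the dissociation scale are unrestricted up to the 4th infusion. CGI, YMRS and BAC-A share the selected visits, but no direction can be claimed for them. Sensitivity, specificity and predictive values degenerate only if treatment-4 response is the predictor, and no predictor time point is named. Time to relapse is affected only if hospitalisation for worsening is censored.

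**Conclusion.** The point holds for MADRS change. As scheduled, that analysis rests on early responders who were not hospitalised before the visit, and it overstates mean improvement relative to all treated patients. Confidence is high for the direction, which needs only a positive correlation between early and later change. It is not high for the size, which rests on the assumed SD, correlation, baseline, cut-off and early response rate. The overstatement is negligible if nearly everyone responds early (0.1-0.2 points), modest at 50% treatment-4 remission (0.7-1.4) and material at 19% (2.2-4.5, with d 20-58% too high). Inflation of the primary remission rate is conditional on the denominator. The rule produces a biased estimate of the quantity the trial is meant to supply, and the core correction is nearly free, so it should be made before the analysis is fixed.

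**What to change.** Leave the treatment-stopping rules as they are.

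1. Add the treatment-4 MADRS to the Study design schedule, and the screening score if it differs from baseline.
2. Define the analysis set as all patients with at least one infusion. Report primary remission on that denominator, with removed or hospitalised patients counted as non-remitters and an exact 95% CI.
3. Report the all-treated MADRS change from a longitudinal model that includes the treatment-4 score with an unstructured covariance. State that it assumes missing at random and estimates change had treatment continued. Show the retained-only paired change beside it, labelled conditional on early response.
4. Report numbers removed, by reason.
5. Do not compute sensitivity, specificity, PPV or NPV with removed patients dropped, or with end-of-study status set by the removal rule. With treatment-4 response as predictor, the first forces specificity to 0%. The second forces sensitivity and NPV to 100%.

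The assessment schedule in C. Approach, the Study design table, the two removal paragraphs and Data analysis must be reconciled.

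**Cost.** Items 1 to 5 need only wording and the listing of a score the rule already requires. The reported effect size will be lower and its interval wider. At n = 30 the model removes bias but is not always more accurate. At ρ 0.4 its root mean squared error is about 4.0 points against 3.5 for the paired result in the 35/40% reduction case, and about equal at 50% treatment-4 remission. It is better at ρ 0.6-0.8 when response is low.

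**Optional, not needed for this point:** voluntary MADRS follow-up after removal, and a sensitivity analysis for hospitalisation removals, which may not be missing at random.

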The *primary objective* of our study is to determine the effectiveness of serial infusions of intravenous (IV) ketamine in adults *with treatment resistant depression (TRD) - diagnosed with either Major Depressive Disorder or Bipolar Disorder* - at a slower infusion time than reported in previous studies. We expect that this approach alongside with the presence of a psychiatrist with Advanced Cardiac Life Support (ACLS) training will eliminate the need for continuing anesthetic monitoring during infusion, thus leading to a more cost-effective intervention. As part of this objective, we plan to recruit 30 individuals with Treatment Resistant Depression and conduct an open label, naturalistic study using slow infusions of ketamine over a time period of 40 minutes. **The duration of this study will be 12 weeks and will include twice weekly infusions over a period of 4 weeks and weekly infusions for the following 4 weeks of the study treatment period (8 weeks). There will also be a 4 week observational period post- treatment.**

Our *hypotheses* are that patients suffering from TRD receiving weekly slow IV infusions of ketamine (0.5 mg/kg) over 40 minutes will:

1. Report similar efficacy and better tolerability than those reported with conventional schemes of 3 infusions per week over a 12 day period.
2. Report less psychiatric side effects measured by changes in test scores on the Montgomery-Åsberg Depression Rating Scale (MADRS), Quick Inventory of Depressive Symptomatology (QIDS) and Young Mania Rating Scale (YMRS) compared to those previously reported with conventional schemes of serial ketamine infusions.
3. Report an almost immediate effect based on the PANSS and Q-LES-Q scales which will be administered after the 40 min infusion period.
4. Report less suicidal ideation measured by changes in scores on the Scale for Suicide Ideations (SSI; Beck et al., 1979), and the Suicide Status Form (SSF; Conrad et al., 2009) scores compared to that previously reported with conventional schemes of serial ketamine infusions.
5. Report a better global outcome of treatment measured by a decrease in scores on in the Clinical Global Impression Scale (CGI; Guy, 1976) score compared to that previously reported with conventional schemes of serial ketamine infusions.
6. Experience less hemodynamic changes in blood pressure and heart rate compared to than those previously reported with conventional schemes of serial ketamine infusions.

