The BAC-A is based on the Brief Assessment of Cognition in Schizophrenia (BAC-S). The BAC-S has been validated both linguistically and psychometrically in a number of psychiatric populations, including patients with schizophrenia and BD (Cuesta et al., 2011; Hill et al., 2013; Kuswanto, Sum, & Sim, 2013; Salgado et al., 2007; Segarra et al., 2011). It has been shown to be as valid and sensitive as a traditional neuropsychological assessment and takes approximately 35 minutes to administer (Keefe et al., 2004; Velligan et al., 2004). Six of the 8 subtests of the BAC-A match those found in the BAC-S. These tests are the Token Motor Task, Symbol Coding, List Learning, Digit Sequencing Task, Category Instances (Animals) and

Controlled Oral Word Association Test (F and S-words), Tower of London (Keefe et al., 2004). In addition to these 6 subtests the BAC-A comprises the Emotion Inhibition Test (a modified version of the Emotional Stroop task (LaMonica, Keefe, Harvey, Gold, & Goldberg, 2010; Williams, Mathews, & MacLeod, 1996)) and the affective auditory verbal learning test (Affective interference test). The latter task is similar to the Affective Auditory Verbal Learning Test (AAVLT) (Snyder & Harrison, 1997). Assessments will be conducted prior to the treatment period, 4, and 8 weeks into the treatment. To avoid potential learning bias we will use parallel versions of the word lists for the Emotion Inhibition Test, Tower of London, and the Verbal Memory Tests to assess cognitive changes over the course of the ketamine treatment.

Study design

We will follow an AB design and clinical/cognitive assessments will be taken at baseline, week 4, week 8, and week 12. Given the preliminary nature of this treatment study this open label trial aims to generate an effect size for a subsequent RCT and/or future grant application. No *a priori* estimates of the power/effect size were therefore calculated.

Timeline	After Each Infusion	Baseline	Week 4	Week 8	Weekly Follow-up Phone Calls	Week 12
SCID-I		X				
Clinical scales (MADRS, CGI, YMRS)		X	X	X	X	X
PANAS, Q-LES-Q, self-report	X					
BAC-A		X	X	X		X
Blood tests/Sample		X	X	X		X
Urine drug test	X	X				

Study sample

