Normality assumptions for continuous variables will be examined. Where appropriate, outliers will be winsorised and log, square root or reciprocal transformations applied to achieve normality if appropriate. If normality cannot not been achieved, either untransformed or dichotomized scores were used. Baseline characteristics will be compared between responders and non-responders with the Mann-Whitney U test for continuous variables and the chi-square test for categorical variables. Changes between two time-points for continuous variables were tested with paired t tests, and associations between continuous variables will be quantified with the Spearman correlation coefficient. Random effects models will be performed to quantify changes in clinical score and its component items over time and to compare temporal differences between eventual responders and non-responders. Splines will be used to determine differences in the pattern of response over time among all patients and to identify the time at which there was no additional improvement in depressive symptoms. Additionally, the relationship between response status between baseline and end of study calculating sensitivity, specificity, and positive and negative predictive values will be reported. Time to relapse for patients who met response criteria at end point will be estimated with the Kaplan-Meier method. Analyses will be performed with IBM SPSS Statistics (version 19; SPSS, Chicago, Illinois) and SAS (version 9.2; SAS, Cary, North Carolina).

Study timetable

Activities	Months											
	1	2	3	4	5	6	7	8	9	10	11	12
Obtain IRB approval at UTHealth and HCPC		x	x									
Set up the Ketamine Ambulatory Clinic at HCPC			x	x								
Start recruiting patients and collecting data					x	x	x	x				
Analyses of initial dataset								x	x	x		
Submit a poster to International meeting with final results									x	x	x	
Submit result to high-impact peer-reviewed journals											x	x

Importance of the knowledge to be gained

Our findings will enhance our understanding of the safety, tolerability and efficacy of ketamine infusion in adults with TRD. Further it will help us understand the feasibility of this treatment in a psychiatric setting. The findings of the present study will also constitute an important foundation for future grant proposals investigating the efficacy of this intervention as a measure of suicide prevention.

*Women and Minority Inclusion in Clinical Research**Inclusion of Women*

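### Data-driven winsorising, transforming or dichotomising makes the planned effect size irreproducible, and winsorising tends to inflate it

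*Combined protocol and SAP*

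**What the plan says.** All points are in the combined protocol and SAP.

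- **Handling of scores (Data analysis).** Normality of continuous variables is examined first. Then, where judged appropriate, "outliers will be winsorised and log, square root or reciprocal transformations applied to achieve normality if appropriate". If normality is still not reached, "either untransformed or dichotomized scores were used".
- **Analyses that use these scores (same section).** "Changes between two time-points for continuous variables were tested with paired t tests". Also, "Random effects models will be performed to quantify changes in clinical score and its component items over time".
- **Purpose (Study design).** "this open label trial aims to generate an effect size for a subsequent RCT and/or future grant application". The funding paragraph under Feasibility again ties the data to effect sizes and power for a larger grant.
- **Size.** "we plan to recruit 30 individuals with Treatment Resistant Depression", in one open-label arm. No power or effect size was calculated in advance (Study design).
- **Primary outcome (end of Background and Rationale).** Remission, judged from the MADRS.

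The plan does not define an outlier, set a winsorising limit, list the variables concerned or say how a transformation is picked. It gives no cut-point and no rule for choosing between the two fallbacks. It does not name the scale on which the effect size will be reported, or provide for a comparison with unaltered scores.

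**The concern.** An extreme but valid MADRS change is information about how variable the response is. Pulling it in before analysis reduces the SD while usually moving the mean only a little, so the ratio of the two rises. That ratio is what a sample-size calculation would use if the effect size is reported as a standardised mean change.

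The other steps cause different trouble. A transformed-scale effect cannot be set beside published MADRS results, although most of the study hypotheses are comparisons with earlier ketamine schedules. Log and reciprocal are undefined at a score of 0, and no offset is stated. Dichotomising throws information away. A paired t test needs near-normal differences rather than normal raw scores, so non-normal raw scores do not by themselves justify any of these steps.

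Because each choice is left open, two competent analysts could take the same 30 patients and report different effect sizes on different scales, and the reader could not tell how much was due to the handling.

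**Working it through.** The plan states no power, SD or effect size, so there is no figure of its own to reproduce. From the documents: 30 patients, one arm, change tested within patients. All distributions and outlier rules below are assumptions. Simulations used at least 20,000 samples per setting, with d = mean change / SD of change.

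**1. Mechanism of winsorising.** The ratio of new to old d is (new mean / old mean) × (old SD / new SD). For normal changes centred near 15 points, clipping one value per tail leaves the mean at 14.99 and takes the average SD from 8.91 to 8.36: 1.00 × 8.91/8.36 = 1.07. The simulated median d rises from 1.687 to 1.797, also a ratio of 1.07.

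**2. Size when only flagged outliers are clipped (true d = 1.0, n = 30).**

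| Change scores | 3-SD rule | 1.5-IQR rule | 2-SD rule |
|---|---|---|---|
| Normal | 1.029 → 1.030, +0.1% | 1.029 → 1.049, +2% | about +3% |
| t, 5 df | 1.061 → 1.075, +1% | 1.061 → 1.156, +9% | about +8 to 9% |

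Repeat runs of the heavy-tailed case differed by up to about 2 percentage points (11% under the IQR rule in one run).

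**3. Size when a fixed number is clipped (n = 30, normal).** Mean d goes from 1.03 to 1.10, 1.18 or 1.27 with 1, 2 or 3 values per tail. The last is 1.27/1.03 = 1.23, and it alters 6 of 30 patients.

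**4. Where inflation fails.** Plant one patient 3.5 SD above the mean and clip by the IQR rule. With an underlying d of 0.2, median d goes from 0.272 to 0.271 and falls in 57% of samples. With an underlying d of 1.0 it goes from 0.956 to 1.009 (+5.5%). With the extreme patient on the non-improving side instead, it goes from 0.757 to 0.839 (+11%).

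**5. Transformation.** Assumed baseline scores had mean 32 and SD 5; post-treatment scores were skewed with mean 12 to 16; 1 was added before log or reciprocal. The median ratio to raw d was 0.91 to 0.96 for square root, 0.77 to 0.87 for log and 0.41 to 0.56 for reciprocal. Other shapes could go the other way.

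**6. Dichotomising.** Take two groups with d = 0.5 split at the midpoint. The proportions are Φ(0.25) = 0.599 and Φ(−0.25) = 0.401. The standardised difference is (0.599 − 0.401)/√(0.599 × 0.401) = 0.198/0.490 = 0.40, about 0.81 of the continuous value. At two-sided 5% and 80% power, a two-arm trial then needs 100 per arm instead of 63. A median split of a normal score keeps 2/π = 0.64 of the information, so 30 patients act like about 19.

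**7. Consequence of inflation for a later trial.** Take a true two-arm d of 0.5, again with two-sided 5% and 80% power. Patients per arm are 2 × (1.96 + 0.84)²/0.5² ≈ 63. Planning on a d that is 5% or 10% too large gives 57 or 52 per arm, with true power of 76% or 72%. This shows proportion only, since a before-after d in one arm is not a between-arm d.

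**8. Sampling error for comparison.** At d = 1.0 and n = 30, SE = √(1/30 + 1/60) = 0.224, so the 95% interval is about 0.56 to 1.44.

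**The case against.** A reader might infer that the whole sequence shrinks the SD, inflates the effect and leaves the later trial too small. The documents do not support that. Dichotomising is one of two fallbacks, not a step that always follows; the other is to leave scores untransformed, which is close to the fix below. Dichotomising attenuates the effect, and the transformations tried lowered it. The net direction of the procedure is therefore unknown, and attenuation would make a later trial too large.

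A reader might also take the fixed-count figures in step 3 as the expected bias. The plan speaks of outliers, and only where appropriate. In normal data a 3-SD rule would rarely be triggered, so those figures describe a much heavier intervention than the text implies.

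Two further points stand. The effect size could turn out to be a remission or response rate, and remission scored from raw MADRS is not touched by any of this. The shifts in step 2 are also well inside the interval in step 8. However, sampling error is visible in a confidence interval, whereas the shift from winsorising is mostly one-directional and does not show in it.

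That log and reciprocal fail at 0 is partly met by the plan's proviso that a transformation be appropriate, and square root works at 0. Mann-Whitney, Spearman and random-effects methods are already planned. None of this supplies the missing rules.

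**Conclusion.** The concern holds in a limited form. The plan permits post-hoc alteration of valid scores in a trial whose product is an effect size, and it does not say on which data or scale that figure will rest. Only winsorising has a predictable direction: with a true d of 1.0 and 30 patients, about 0 to 3% inflation for normal changes and 1 to 9% for t (5 df) changes under flagged-outlier rules, and more under fixed-count clipping. With a small effect it may not inflate at all.

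These sizes rest on assumed distributions and outlier rules, and on the effect size being a standardised mean change. Transformation makes the result non-comparable in an uncertain direction, and dichotomising costs information. The primary outcome is unaffected if remission is scored from raw MADRS, which the plan does not state. It is worth correcting because the correction is cheap, not because the bias is shown to be large.

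**What to change.** In Data analysis, replace the winsorise, transform or dichotomise rule with the following:

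- Estimate change and its effect size on the original scale from all observed values, using the planned random-effects model with robust or bootstrap confidence intervals. State which SD is used to standardise, and report the mean change in points beside it.
- Delete the dichotomising fallback. Remission and response stay as clinical endpoints in their own right, scored from raw MADRS.
- Report winsorised or transformed results only as labelled sensitivity analyses, with the outlier rule, limit and any offset written down before the data are examined.
- If a non-parametric check of change is wanted, use the Wilcoxon signed-rank test.

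The cost is analysis wording, with no extra patients, visits or data. The downside is a slightly smaller effect size and somewhat wider intervals than winsorised scores would give.
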